## **Study Protocol**

**Cardiovascular effects after CPAP withdrawal for obstructive sleep apnea**

**NCT number: 02329470**

**Document date: October 2013**

## Background

Sleep apnea is common in the population and in a newly published population study of 400 women we found that 50% of them had sleep apnea and 20% had moderate and severe sleep apnea (1). More than 30,000 people in Sweden are being investigated per years for sleep apnea. The most common and effective treatment is CPAP (2-4). Many people use CPAP all and whole nights while others sometimes sleep without CPAP one or a few nights a week. However, it has not been studied whether it is dangerous to sleep without CPAP for a few nights.

Blood pressure and heart rate rise due to a stress surge and oxygenation drops during an obstructive apnea. Patients with obstructive sleep apnea are at increased risk of cardiovascular disease such as hypertension, myocardial infarction, stroke and premature death (5-6). We have previously shown that nocturnal angina is triggered by obstructive sleep apnea (7). Systemic inflammation and impaired blood vessel function including endothelial function are also associated with obstructive sleep apnea (8).

The arterial stiffness of the central arteries is mainly determined by the compliance of the aorta and increases with an impaired function of elastic fibers. Arterial stiffness increases with age, diabetes mellitus, inflammation, hypertension, obesity, smoking, cholesterol levels and atherosclerotic disease (9). Increased arterial stiffness is an independent risk factor for morbidity and death in cardiovascular disease (10). Arterial stiffness measurement is a validated and widespread method to assess endothelial function.

Many patients sometimes sleep without their CPAP. It is important from a clinical point of view to know if the cardiovascular system is affected by CPAP withdrawal for some nights.

## Aims

The primary aim was to investigate the cardiovascular effects of short-term CPAP withdrawal for five nights in women and men with obstructive sleep apnea.

## Design

Randomized, parallel controlled trial

## Inclusion Criteria

Men and women aged 18 years old with moderate to severe obstructive sleep apnea and successful CPAP treatment for 2 months to 2 years with good compliance (mean CPAP use of >4 hours/night) during the last month before inclusion. Signed written consent to participate in the study.

## Exclusion Criteria

Apnea hypopnea index >10 with CPAP treatment, heart infarction within 3 months prior to study participation, severe dementia, determined by study personal having psychological or physical hinder to participate in the study

## Randomization

50 patients are randomized to sleep 5 days without CPAP and 50 patients to continue with CPAP treatment during the trial. Randomization is done by a person outside the study.

## Primary outcomes

Arterial stiffness measured with pulse wave velocity, and 24-hour blood pressure.

## Secondary outcomes

Effects of gender on outcome. Effects on brain natriuretic peptide, apnea-hypopnea index, oxygen desaturation-index, urine-catecholamines, blood lipids, C-reactive protein, glucose metabolism (S-glc, HBA1c), serum-insulin, serum creatinine, hemoglobin, daytime sleepiness (ESS, KSS), lung function (FVC, FEV1), airway inflammation (exhaled NO) Procedures: Sleep apnea investigation while patients are treated with CPAP for one night. Urinary samplings during the same night. They are also investigated with 24 h blood pressure measurements. Blood samples are taken fasting in the morning followed by measuring the arterial stiffness (Vicorder, Skidmore Medical UK) including pulse wave analysis using sphygmomanometer (Omron Japan). The same investigations are done at follow-up 5 days later where half of the patients have continued using CPAP treatment and half of them has slept without CPAP.

## Power calculation

It was estimated that 90 patients, 45 in each group, would be needed to detect a mean (SD) blood pressure difference of 3 (5) mm Hg with a power of 80% and a significance level of 5%. It was estimated that 34 patients, 17 in each group, would be needed to detect a mean (SD) difference of 1 (1) m/s in pulse wave velocity with a power of 80% and a significance level of 5%.

## Procedures

100 patients fulfilling inclusion criteria are invited to the trial after informed consent for baseline and follow-up investigations.

Baseline investigations Day 1 Patients are given a questionnaire. They are given blood pressure monitoring, (ABPM Medical 90217 ambulatory blood pressure monitor, Spacelab) for 24 hours starting at 8-9 AM. They are also given sleep apnea investigation equipment (Embletta, X 10 system, Embla systems, ResMed) for ambulatory use during the following night, and a container for urinary sampling during the night for measurements of urine norepinephrine.

Day 2 Fasting on arrival. Return of the 24-h blood pressure recording, the sleep apnea recording and the urine sampling container.

Blood samples at 08.15 am after resting for 15 minutes. Arterial stiffness is measured using arterial pulse wave velocity, radial artery applanation tonometry and office blood pressure. After resting, the measurements start at 8.30 AM in a room with a temperature of 24°C. Pulse wave velocity (Vicorder, Skidmore Medical, Bristol, UK) is measured in the supine position. The augmentation index is derived from pulse wave

analysis obtained from radial artery applanation tonometry on the right arm (SphygmoCor, AtCor Medical, Sydney, Australia).

Lung function and exhaled NO measurements, ECG. Breakfast at around 10.00 am. CPAP time counter check Patients are then randomized with a ration of 1:1 to continue with CPAP or not for the following 5 nights.

Follow-up measurements Day 6 They are given blood pressure monitoring, (ABPM Medical 90217 ambulatory blood pressure monitor, Spacelab) for 24 hours a starting at 8-9 AM. They are also given sleep apnea recorder (Embletta, X 10 system, Embla systems, ResMed) for ambulatory use during the following night, and a container for urinary sampling during the night (urine norepinephrine).

Day 7 Fasting on arrival. CPAP time counter check Return of the 24-h blood pressure recording, the sleep apnea recording and the urine sampling container.

Blood samples at 08.15 am after resting for 15 minutes. Arterial stiffness is measured using arterial pulse wave velocity, radial artery applanation tonometry and office blood pressure. After resting, the measurements starts at 8.30 AM in a room with a temperature of 24°C. Pulse wave velocity (Vicorder, Skidmore Medical, Bristol, UK) is measured in the supine position. The augmentation index is derived from pulse wave analysis obtained from radial artery applanation tonometry on the right arm (SphygmoCor, AtCor Medical, Sydney, Australia).

Lung function and exhaled NO measurements, ECG. Breakfast at around 10.00 am. The trials ends and patients are told to continue with CPAP as usual.

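### Nothing keeps the arm from the person who measures Day 7 pulse wave velocity, and the Day 7 list puts the CPAP counter check, which in effect shows the arm, before that measurement

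*Protocol*

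**What the plan says.** The Primary outcomes section names "Arterial stiffness measured with pulse wave velocity, and 24-hour blood pressure". Under Procedures, pulse wave velocity is measured at the clinic with the patient supine, at baseline on Day 2 and at follow-up on Day 7.

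On who may know the allocation there is one sentence, in the Randomization section: "Randomization is done by a person outside the study". The Design section calls the trial randomized, parallel and controlled. No section mentions blinding or masking of anyone.

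The CPAP time counter is checked twice, at different points of the two visits:

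- **Day 2:** after the measurements and just before allocation: "Breakfast at around 10.00 am. CPAP time counter check Patients are then randomized with a ration of 1:1".
- **Day 7:** among the arrival steps: "Day 7 Fasting on arrival. CPAP time counter check Return of the 24-h blood pressure recording". Blood sampling at 08.15 follows, then arterial stiffness: "After resting, the measurements starts at 8.30 AM". The visit closes with "Breakfast at around 10.00 am. The trials ends and patients are told to continue with CPAP as usual".

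**The concern.** An outside randomizer addresses who allocates. It does not govern what the person measuring on Day 7 knows five nights later. Patients cannot be masked to whether they sleep with CPAP, so masking the measurer is the protection still available for an outcome taken by staff at the visit. The protocol does not provide it, and its listed Day 7 order brings out information that separates the arms shortly before the measurement.

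Randomization does not remove this risk. Baseline is measured before allocation, so knowledge of the arm can act only on the follow-up value, and any influence would enter the between-arm comparison directly. The Significance section also records that earlier studies found CPAP beneficial for arterial stiffness, so a measurer who knows the arm has a direction to expect. The trial's answer on arterial stiffness rests on this measurement.

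**Working it through.** **1. Inputs**

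- Qualifying CPAP use (Inclusion Criteria): "good compliance (mean CPAP use of >4 hours/night) during the last month before inclusion".
- Counter readings on Day 2 and Day 7 (Procedures).
- Allocation to continue CPAP or not for the 5 nights after Day 2 (Procedures).
- Assumption: the counter shows accumulated hours, and the Day 2 reading is at hand on Day 7.

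**2. Nights between the readings**

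The nights of Days 2, 3, 4, 5 and 6 make 5, which reproduces the protocol's own figure.

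**3. How clearly the counter separates the arms**

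Expected advance = hours per night × 5 nights.

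| Patient | Hours per night | Advance over 5 nights |
|---|---|---|
| Continues CPAP at the qualifying use | > 4 | > 20 h |
| Continues CPAP, lower use (assumed) | 2 | 10 h |
| Continues CPAP, lower use (assumed) | 1 | 5 h |
| Follows allocation to no CPAP | 0 | 0 h |

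Even at an assumed 1 to 2 hours per night in the continuing arm, the gap is 5 to 10 hours. The reading separates the arms as far as patients follow their allocation.

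**4. Order of steps on the two visits**

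| Step | Day 2 | Day 7 |
|---|---|---|
| Counter check | after measurements and breakfast | with the arrival steps |
| Arterial stiffness | before the counter check | after the counter check |
| Allocation | end of the visit | already made |

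At baseline no arm exists when the measurement is taken. At follow-up the arm exists and, in the listed order, can be read off before it.

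**5. Other routes to the same knowledge**

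The arm may become known to staff when patients are randomized at the end of Day 2, at the Day 6 contact ("Follow-up measurements Day 6 They are given blood pressure monitoring"), or from the patient. The counter is one route among several.

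**6. Which outcomes are exposed**

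The risk concerns measurements taken at the Day 7 visit: pulse wave velocity first, and also tonometry, lung function and exhaled NO. The 24-hour blood pressure is less exposed because an ambulatory monitor records it. That recording starts at 8-9 AM on Day 6 and so ends at 8-9 AM on Day 7. Fifteen minutes' rest before blood at 08.15 implies arrival by about 08.00 (08.15 − 15 min), so up to about 60 minutes of it may remain on arrival. It is therefore largely, but not necessarily wholly, complete before the visit.

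**The case against.** The strongest reply is that this is mostly silence: the protocol promises no masking, so it breaks no promise. The one thing it fixes, the place of the counter check, would unmask the measurer only through a chain that the text does not supply. The check would have to take place before 8.30, though it has no clock time. The reader would have to be, or inform, the measurer, though neither is named. The counter would have to show accumulated hours, and the Day 2 value would have to be available. The arm can also leak by other routes, so the order of the list adds little. Day 2 is a weak precedent, because no arm exists there until after the check. Finally, pulse wave velocity and exhaled NO come from instruments, and the documents do not say how far an operator can influence them.

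Much of this stands as a limit. The order is the natural reading of the list and not a timed instruction; the reader and the measurer may be different people; the size of any bias is unknown; Day 2 shows only that a later check is practicable. Two things survive. Following the list as written allows the arm to be seen before a primary outcome is measured, with no instruction to prevent it. And the existence of other routes argues for masking the measurer, not for leaving the matter open. A statistical analysis plan would not cure it: what the measurer knows is settled at the visit, and analysis cannot restore masking afterwards.

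**Conclusion.** The point holds as an avoidable risk of bias in one of the two primary outcomes, not as a contradiction. No text keeps the allocation from the person measuring Day 7 pulse wave velocity, and the listed order places a step that in effect shows the arm ahead of it. The counter gap is more than 20 hours against 0 at qualifying use, and 5 to 10 hours against 0 under the assumed lower use. Those figures say how readable the arm is; they do not measure bias, for which the documents give no basis. The conclusion assumes that the list order is the order of conduct, that the counter shows accumulated hours that can be compared with Day 2, and that patients broadly follow their allocation. Without the counter, the lack of any masking of the measurer would remain. The change should be made; confidence is medium.

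**What to change.** **Main change.** State that whoever takes the Day 7 measurements is not told the allocation or the counter result from randomization onward.

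**Supporting changes.**

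- Move the Day 7 counter check to after the arterial stiffness, lung function and exhaled NO measurements, in the place after breakfast that it already has on Day 2.
- Ask patients not to reveal their arm until the Day 7 measurements are finished.

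Moving the check alone is not enough, because of the other routes.

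**Cost.** Two sentences of instruction and one reordered step, with no added visit or procedure. The protocol gives no staffing information. If one person both tells patients their allocation and measures, those tasks would have to be split; the use of an outside person for randomization makes a split plausible. Masking would stay imperfect because patients know their arm, so the risk is reduced and not removed.

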#### Significance

Previous studies report that CPAP treatment has a beneficial effect on arterial stiffness. It is unknown whether it is dangerous to sleep without CPAP for a few days, which many patients with obstructive sleep apnea sometimes do. We will investigate whether it is hazardous for patients to be without CPAP for a few days by examining arterial stiffness and 24-hour blood pressure after 5 nights without CPAP in a randomized controlled trial.

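### Does the 24-hour blood pressure recording miss the stated exposure because it starts after four nights without CPAP rather than five?

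*Protocol*

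**What the plan says.** The protocol (the only document at hand) describes the exposure and its timing in several places.

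- **Aims:** the trial studies the "cardiovascular effects of short-term CPAP withdrawal for five nights".
- **Primary outcomes:** "Arterial stiffness measured with pulse wave velocity, and 24-hour blood pressure", with no timing attached.
- **Secondary outcomes** (which also contains a short account of procedures): "The same investigations are done at follow-up 5 days later".
- **Procedures, Day 2**, after the morning tests and breakfast: "Patients are then randomized with a ration of 1:1 to continue with CPAP or not for the following 5 nights".
- **Procedures, follow-up:** "Follow-up measurements Day 6 They are given blood pressure monitoring", for 24 hours from 8-9 AM. On Day 7 the entry is "Return of the 24-h blood pressure recording, the sleep apnea recording and the urine sampling container", and for arterial stiffness "After resting, the measurements starts at 8.30 AM in a room with a temperature of 24°C".
- **Significance:** the question is to be answered "by examining arterial stiffness and 24-hour blood pressure after 5 nights without CPAP in a randomized controlled trial".

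**The concern.** The Significance section gives both primary outcomes the same exposure: five completed nights off CPAP. Only pulse wave velocity, taken on the morning of Day 7, meets that description. The monitor goes on a day earlier, so nearly all waking readings follow four nights, and the sleeping readings are taken during the fifth.

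If this mattered, three things would be at stake:

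- A blood pressure result would be reported as a five-night effect when much of it reflects four nights.
- A single 24-hour mean would combine carry-over into the day with pressure during untreated sleep. The Background section says that blood pressure rises during an obstructive apnea, so a raised mean could come from the night alone.
- If the effect accumulates night by night, the recording would capture less than the full effect and power would be lower than planned.

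**Working it through.** **Counting the nights** (all times from Procedures)

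| Event | Time | Nights completed off CPAP |
|---|---|---|
| Randomisation | Day 2, after breakfast | 0 |
| Monitor fitted | Day 6, 8-9 AM | 4 (Day 2-3, 3-4, 4-5, 5-6) |
| Fifth night | Day 6-7 | inside the recording |
| Monitor returned; pulse wave velocity measured | Day 7, morning | 5 |

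The stated figure of five is reproduced for pulse wave velocity. For blood pressure it is four at the start of the recording and five by its end.

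**Splitting the 24 hours.** The protocol gives no bedtimes, so sleep of 6 to 9 hours is assumed. Then:

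- 13 to 16 hours (54% to 67%) precede the fifth night;
- 6 to 9 hours (25% to 38%) fall during it;
- 1 to 3 hours (4% to 13%) follow it.

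**Checking the other sections against this timetable.** The Aims refer to withdrawal for five nights, which the timetable delivers. The Primary outcomes section gives no timing. Follow-up five days later fits both outcomes: Day 1 to Day 6 for blood pressure (6 - 1 = 5) and Day 2 to Day 7 for pulse wave velocity (7 - 2 = 5). Only the Significance sentence is out of step.

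**Sample size as planned.** Inputs from Power calculation: difference 3 mm Hg, SD 5, power 80%, significance level 5% (two-sided assumed). With n = 2(1.96 + 0.84)² × (5/3)², the normal approximation gives 44 per group. The t-test version gives 44.6, rounded up to the 45 stated. For pulse wave velocity (1 m/s, SD 1) the results are 16 and 16.7, the latter rounded up to the 17 stated. Both figures reproduce, and neither depends on a night count.

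**Power if the effect accumulates.** Two assumptions are needed: the effect grows linearly by night, so that four nights carry 4/5 = 0.8 of it, and the 3 mm Hg is the effect after five completed nights. With 16 waking and 8 sleeping hours:

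- fraction captured = (16/24) × 0.8 + (8/24) × 1.0 = 0.867;
- effect = 3 × 0.867 = 2.60 mm Hg, and 2.60/5 = 0.52 SD;
- t-test power = 68.5% with 45 per group (against 80%) and 73.1% with 50 per group (against 84%).

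This weighting counts every waking hour as following four nights. Giving the hours after waking on Day 7 the full effect raises power with 45 per group to about 68% to 71% over the assumed sleep range. If the effect is immediate, the fraction is 1 and nothing is lost.

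**The case for a change.** The best case for a change is that the night count is right and cannot be read away: no interpretation of the day numbers completes five nights before Day 7. Blood pressure is a primary outcome, the trial asks whether a few nights without CPAP are hazardous, and a conclusion worded as pressure after five nights could suggest a sustained daytime effect that the recording need not show. Correcting the wording and adding daytime and night-time means would cost almost nothing, since the data are already collected.

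The count stands, and so does the looseness of the phrase. The rest carries less weight.

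- Significance is a rationale paragraph. Procedures gives days, clock times and duration, and an analyst or reader would work from those.
- Any 24-hour mean mixes waking and sleeping pressure, whenever it is recorded. Separate day and night summaries are commonly left to the statistical analysis plan, which is not shown, and nothing in the protocol rules them out.
- A 24-hour recording begun only after five completed nights would run into a sixth night. That night would either extend the exposure beyond five nights or be spent back on CPAP. Placing the recording over the last day and night of the withdrawal is a fair trade-off.
- The power loss rests on a linear build-up that no section supports. Power calculation gives 3 mm Hg as the difference to be detected and does not tie it to a number of nights. The Background's remark about pressure rising during an apnea points to at least part of the effect being acute, and the fifth-night readings capture that part.

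**Conclusion.** No change to the plan follows. The phrase in Significance is imprecise for one of the two primary outcomes: the blood pressure recording covers the last day and night of a five-night withdrawal, starting after four completed nights and ending on the morning after the fifth. That is a clerical looseness of one night in a non-operative paragraph. It does not conflict with the Aims, the outcome sections or the timetable.

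The inference is unaffected. Both arms have the same schedule, and baseline has the same layout (monitor from Day 1, pulse wave velocity on Day 2), so the comparison between arms is unbiased. The sample sizes reproduce as stated. The lower power figures hold only under two assumptions that the protocol does not make, so no power loss is shown. The share of the recording that precedes the fifth night (54% to 67%) rests on assumed sleep of 6 to 9 hours, but the conclusion does not depend on it. Authors reporting the result can describe the recording window from Procedures, and doing so changes no measurement or analysis.

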#### Ethical considerations

Blood tests on the patients and this can cause some discomfort, but all blood sampling is done by experienced staff. Measuring arterial stiffness does not cause any discomfort.

#### Sex perspective

Both men and women of different ages are included in the study. We aim analyze women and men in separate.

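### Gender effect is a secondary outcome, but the only stated method, separate analyses of women and men, does not compare the sexes

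*Protocol*

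**What the plan says.** The protocol's Secondary outcomes section opens with "Effects of gender on outcome". The Sex perspective section notes that "Both men and women of different ages are included in the study" and continues "We aim analyze women and men in separate". Nothing else in the protocol says how sex enters the analysis.

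The primary outcomes are "Arterial stiffness measured with pulse wave velocity, and 24-hour blood pressure". Under Randomization, "50 patients are randomized to sleep 5 days without CPAP and 50 patients to continue with CPAP treatment during the trial". No target share of women, stratification by sex or sample size by sex is given. The Power calculation section covers only the overall comparison of the two arms.

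**The concern.** The secondary outcome concerns effect modification: whether stopping CPAP affects women and men differently. The quantity that answers it is the effect in women minus the effect in men, with its uncertainty. Separate analyses stop one step earlier, at two effects that are never set against each other.

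The protocol does not say how those two results become a statement about gender. A common practice is to note that one sex is significant and the other is not. That contrast is not evidence of a sex difference, because each half-sample has limited power and the two can disagree by chance. It also fails in the other direction: when both sexes are significant, a real difference in size goes unseen.

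The Significance section asks whether a few days without CPAP is hazardous. A chance pattern of significance in one sex only could be reported as showing that the other sex is spared.

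**Working it through.** **Inputs from the protocol**
- 50 patients per arm (Randomization).
- Blood pressure: difference 3 mm Hg, SD 5. Pulse wave velocity: difference 1 m/s, SD 1. Power 80%, significance level 5% (Power calculation).

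**Assumptions**
- Two-sided tests.
- The sex split is not given, so two are shown: 50/50 (25 women and 25 men per arm) and 30/70 (15 women and 35 men per arm), with the arms balanced within sex.
- The same SD in both sexes, and no gain from baseline adjustment.

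**Step 1: reproduce the plan's own sample sizes.** Two-sample t-test, noncentral t. For d = 3/5 = 0.6, 45 per group gives power 0.804. For d = 1/1 = 1.0, 17 per group gives 0.807. Both agree with the 90 and 34 patients in the protocol, so its effects and SDs are a sound basis.

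**Step 2: power within each sex, same true effect in both.** The noncentrality is d × √(n/2), with n per arm within sex.

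| True effect | d | n = 25 | n = 15 | n = 35 |
|---|---|---|---|---|
| BP 2 mm Hg | 0.4 | 0.283 | 0.185 | 0.378 |
| BP 3 mm Hg (planned) | 0.6 | 0.547 | 0.355 | 0.697 |
| BP 4 mm Hg | 0.8 | 0.791 | 0.562 | 0.910 |
| PWV 1 m/s (planned) | 1.0 | 0.934 | 0.753 | 0.985 |

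**Step 3: chance that exactly one sex is significant although the sexes do not differ.** The sexes are independent samples, so this is p₁(1 − p₂) + p₂(1 − p₁).

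| True effect in both sexes | 50/50 | 30/70 |
|---|---|---|
| BP 2 mm Hg | 40.6% | 42.3% |
| BP 3 mm Hg | 49.6% | 55.7% |
| BP 4 mm Hg | 33.0% | 44.9% |
| PWV 1 m/s | 12.4% | 25.5% |
| No effect | 9.5% | 9.5% |

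For example, BP 3 mm Hg at 30/70: 0.355 × 0.303 + 0.697 × 0.645 = 0.557. With no effect: 2 × 0.05 × 0.95 = 0.095.

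A test of the interaction is wrong about 5% of the time in every row. A simulation of 200,000 trials (BP 3 mm Hg, 50/50) gave 49.6% discordant and an interaction significant in 5.0% overall. Among the discordant trials it was significant in 9.6%.

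**Step 4: the opposite error.** Suppose the true pulse wave velocity effects were 2 m/s in one sex and 1 m/s in the other, at 50/50. Both sexes are significant in 1.000 × 0.934 = 93% of trials, so contrasting p-values shows nothing. The interaction test has 70% power for that 1 m/s difference.

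**Step 5: what the interaction can detect.** SE = SD × √(2/w + 2/m), with w women and m men per arm. The difference detectable with 80% power is 2.80 × SE.

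| | SE | Power for a sex difference equal to the planned effect | Detectable at 80% power |
|---|---|---|---|
| BP, 50/50 | 5 × √(2/25 + 2/25) = 2.00 mm Hg | 31.8% (3 mm Hg) | 5.6 mm Hg |
| BP, 30/70 | 5 × √(2/15 + 2/35) = 2.18 mm Hg | 27.5% (3 mm Hg) | 6.1 mm Hg |
| PWV, 50/50 | 0.40 m/s | 69.7% (1 m/s) | 1.12 m/s |
| PWV, 30/70 | 0.436 m/s | 62.1% (1 m/s) | 1.22 m/s |

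**The case against.** The strongest objection is that this is detail a protocol may leave to the SAP, which is not shown. The protocol names no test or model even for its primary outcomes, the sentence on sex is worded as an aim, and reporting effects by sex is compatible with an interaction test. That would settle the matter if the protocol were silent. It is not: it names an outcome and, separately, one method bearing on it, and the method does not answer the outcome. An SAP may add the comparison, but the protocol sentence would still need correcting.

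A second objection is that women and men are independent samples, so the two effects can be subtracted and the standard error of the difference follows from theirs. That is true, and it is how the standard errors in the working arise. Separate analysis therefore does not rule out a comparison, but the subtraction is a further step that the protocol does not state.

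Third, the discordance rates depend on someone contrasting p-values, which the protocol does not prescribe, and the example of 2 m/s in one sex uses twice the planned effect. Both points stand. Those figures illustrate a risk; they do not measure a rule in the plan. The mismatch itself does not depend on them.

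Finally, the interaction has low power for blood pressure. That is correct, and it is a reason to show the difference with an interval. Two separate p-values would hide the same uncertainty.

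**Conclusion.** The concern holds. A named secondary outcome is paired with a stated method that by itself gives no estimate of the quantity asked for. If the separate results are compared by significance, about half of trials (50% to 56%) would suggest a sex difference in blood pressure when none exists at the planned effect. For pulse wave velocity it would be 12% to 25%. These figures assume 50 patients per arm, a share of women between 30% and 50%, the protocol's SDs in both sexes, and a reader who contrasts p-values.

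The primary comparison of the arms is untouched. The correction should be made because it costs almost nothing, but the trial's main result does not depend on it.

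**What to change.** Replace the sentence on separate analysis under Sex perspective with text such as:

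> The effect of gender on each primary outcome (pulse wave velocity, 24-hour blood pressure) is estimated as the arm-by-sex interaction with its 95% CI, from one model in all randomized patients with arm, sex, arm-by-sex and the baseline value. Effects in women and in men are reported with 95% CIs from the same model, descriptively. The interaction is exploratory.

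Add the sex difference detectable with 80% power before any gain from baseline adjustment: about 5.6 mm Hg and 1.1 m/s with equal numbers of women and men, or 6.1 mm Hg and 1.2 m/s with 30% women. The essential part is the between-sex difference with its interval; the joint model and baseline term are a convenient and efficient way to obtain it.

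The cost is a few sentences, with no extra patients, visits or measurements, since baseline values are already collected. The downside is that the plan must admit that the gender question is exploratory and that the analysis would miss about two thirds or more of true 3 mm Hg sex differences in blood pressure (1 − 0.318 = 68% at 50/50; 1 − 0.275 = 72.5% at 30/70).
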